12.2	Conflict of Interest	36
12.3	Participant Stipends or Payments	36
13	Publication and Data Sharing Plan	36
14	References	36
15	Attachments.....	40
16	Protocol Signature Page.....	41

List of Abbreviations

CRF – case report form

CHPS - Center for Human Phenomic Science (CHPS)

IRB – Internal Review Board

EC – Ethics Committee

CMC – carboxymethylcellulose

Study Summary

Title	Functional Research on Emulsifiers in Humans
Short Title	FRESH Study
Protocol Number	828422
Phase	Not applicable
Methodology	Controlled feeding experiment
Study Duration	161 days
Study Center(s)	1
Objectives	
Establish a tractable and physiologic means of administering and measuring CMC consumption and its metabolic impact in healthy volunteers.
 
Examine extent to which CMC consumption impacts human gut microbiota composition, gene expression, and/or localization.
 
Explore effects of CMC consumption on a range of inflammatory and metabolic parameters that characterize metabolic syndrome.

Number of Participants	20
Diagnosis and Main Inclusion Criteria	Healthy volunteers
Study Product, Dose, Route, Regimen	Participants will be randomly assigned to receive 0 or 15 gm per day of carboxymethylcellulose in 6 divided doses baked in chocolate brownies and served in sorbet
Duration of administration	11 days
Reference therapy	None
Statistical Methodology	Determination of the effect of CMC consumption on the fecal and mucosal microbiome composition and inflammatory and metabolic parameters. Comparison of microbial metabolites across diets (with CMC versus without CMC).

1 Introduction

This document is a protocol for a human research study. This study is to be conducted according to US and international standards of Good Clinical Practice (FDA Title 21 part 312 and International Conference on Harmonization guidelines), applicable government regulations and Institutional research policies and procedures.

1.1 Background

The human intestine is home to some 100 trillion microorganisms. The density of bacterial cells in the colon has been estimated at 10^{11} to 10^{12} per ml, which makes the colon one of the most densely populated microbial habitats known on earth. The genome size of this pool of intestinal microbes is estimated to exceed the size of the human nuclear genome by two orders of magnitude¹. There are far more total cells in the gut microbial population than human cells in our bodies--indeed, it has been stated that "there are more of them in us than us"^{2 1, 3}.

The great majority of these gut bacterial species have not been cultured outside the human host, so most species are little studied. Recent advances in scientific methods have allowed for new surveys of the intestinal microbiota using DNA sequencing of uncultured communities^{1, 4, 5} or microarray-based methods⁶. Many of these studies used 16S ribosomal DNA sequences to query the different bacterial taxa, since 16S sequences are similar enough to allow amplification of most bacterial species with single primer pairs, but diverse enough to allow "finger printing" of taxa to relatively fine taxonomic levels⁷. Such studies have revealed that major bacterial phyla in the human gut include *Bacteroidetes*, *Firmicutes*, *Proteobacteria* and various minor groups. Other recent studies extended this analytical approach by sequencing fragments of bulk genomic DNA from intestinal microbiota instead of 16S DNA^{3, 8-11}. Metagenomic analysis allows inferences to be made about the community taxonomy and the metabolic pathways in the intestinal microbiota inferred from the genes present. For example, the Gill et al. study¹⁰ disclosed that the intestinal microbiota contribute unique pathways for metabolism of glycans, amino acids, xenobiotics, methanogenesis, vitamins, isoprenoids, and other compounds.

When maintained in a stable manner, at an appropriately safe distance from gut epithelial cells, the microbiota provides benefits to the host, especially in terms of energy harvest, pathogen exclusion, and promotion of immune development. In contrast, disturbance of the microbiota-host relationship can drive chronic gut inflammation that can promote an array of chronic inflammatory diseases including metabolic syndrome. While host genetics are an important determinant of the host-microbiota relationship, the dramatic increase in incidence of numerous chronic inflammatory diseases, including inflammatory bowel disease (IBD) and metabolic syndrome over the last 60 years amidst relatively constant genetics, and highlights the importance of understanding how non-genetic factors such as diet might alter the microbiota-host relationship to promote gut inflammation. Consequently, we and others have focused on how differences in macronutrient consumption influence the microbiota. However, dietary patterns can also be characterized by constituents other than macro and micronutrients. Post-mid-20th century dietary changes include consumption of an array of synthetic compounds that are added to many processed foods. The biologic effect of these food additives are not well described, particularly

their potential to influence microbiota composition and/or its interaction with the host. One particularly disconcerting class of compounds are synthetic dietary emulsifiers including polysorbate 80 (P80) and carboxymethylcellulose (CMC). These detergent-like compounds, which are incorporated into a variety of processed foods, are not well-absorbed, thus allowing them to interact with the microbiota and gut mucosa. We have recently shown that, in mice, consumption of P80 and CMC, alters microbiota composition, have pro-inflammatory potential and promote microbiota encroachment into the colonic mucosa, low-grade inflammation, and metabolic syndrome¹. However, it is not known whether these compounds have similar effects in humans. Addressing this critically important question is the central goal of this study. Our initial focus will be on CMC, which, despite not having been tested in humans and not widely studied in animals, has "generally regarded as safe (GRAS)" status from the US FDA, allowing it to be widely and unrestrictedly used in a broad variety of processed foods.

1.2 Investigational Agent

CMC will be purchased from Modernist Pantry who supplies CMC to small bakeries throughout the United States.

1.3 Preclinical Data

This proposal seeks to address the post-mid-20th century increased incidence of chronic inflammatory diseases of the intestine. Crohn's disease and ulcerative colitis, collectively referred to as the inflammatory bowel diseases (IBD), are debilitating diseases that may afflict up to 3 million Americans¹². Like many immune-mediated diseases, the incidence of IBD is increasing in the US and elsewhere at rates far in excess of that expected by genetic drift. A milder but much more common form of gut inflammation referred to as "low-grade" inflammation, is defined by modestly elevated pro-inflammatory gene expression amidst a lack of histopathologically-evident inflammation¹³. Such low-grade inflammation associates with, and may promote, metabolic syndrome, which is a group of interrelated metabolic disorders including obesity, insulin resistance, hyperglycemia, hyperlipidemia, and hepatic steatosis¹⁴. Humanity is facing an epidemic of metabolic syndrome, and its downstream consequences, including type 2 diabetes, cardiovascular disease, and liver dysfunction that threaten to overwhelm the world's healthcare systems and economies thus making it a top public health priority in dire need of investigation. Our research suggests that IBD, metabolic syndrome, and other chronic inflammatory diseases may share common underlying causes, including a disturbed host-microbiota relationship. In accord with this notion, recent studies demonstrate that infections in infants increase likelihood of developing both IBD¹⁵ and obesity¹⁶.

Thus, better understanding of factors that can alter the host-microbiota relationship is of paramount importance. Many candidate factors can be reasonably envisaged to have impacted the microbiota (e.g. antibiotics, polymers such as BPA, pollutants, enhanced sanitation, etc.). Recent studies suggest that some commonly used dietary emulsifiers, which are detergent-like molecules that are incorporated into most processed foods to improve texture and stability, may be one specific contributor to the increased prevalence of chronic inflammatory diseases^{17, 18}. We reported that feeding mice CMC and P80 results in a microbiota that encroaches upon the epithelium and has inherently greater potential to activate host pro-inflammatory signaling¹⁹. Such alterations promote

chronic low-grade inflammation and a metabolic syndrome-like phenotype in mice and increased incidence of severe colitis in mice that are genetically pre-disposed to this disorder. Investigation of these commonly consumed but poorly studied synthetic compounds to determine their impact on human biology, in a manner analogous to our mouse studies, is of the utmost significance to human health.

1.3.1 Risk-Benefit Balance

The risks associated with participating in this controlled feeding experiment are low. The diets will be constructed to meet all nutritional requirements. The CMC will be purchased from Modernist Pantry and is the same as that which is sold to small bakeries throughout the United States. Thus, consumption of the study diet entails no greater risk than consumption of a typical American diet outside of the study procedures.

Participants will undergo phlebotomy and sigmoidoscopy with biopsy. There is a small potential risk for complications of sigmoidoscopy, including bleeding and perforation. The risks of these complications are estimated to be less than 1% for bleeding and less than 0.1% for perforation. Patients with contraindications to biopsy will be excluded. The risks of phlebotomy include bleeding, infection, phlebitis, and fainting. As with all research, there is a small risk of loss of confidentiality. Participants may also experience some discomfort associated with eating a limited diet for 14 days. Participants may also feel tired and/or discomfort from staying in the hospital for the 11 day inpatient stay.

In summary, the risk of serious or severe adverse events is likely extremely low. While there is no direct benefit expected for the participants, the balance of the participants' risk vs. the knowledge to be gained is believed to be favorable.

2 Study Objectives

The specific aims for our proposal are:

1. Establish a tractable and physiologic means of administering and measuring CMC consumption and its metabolic impact in healthy volunteers.
2. Examine extent to which CMC consumption impacts human gut microbiota composition, gene expression, and/or localization.
3. Explore effects of CMC consumption on a range of inflammatory and metabolic parameters that characterize metabolic syndrome.

3 Study Design

3.1 General Design

This is a randomized double-blind, controlled feeding experiment examining the effect of CMC on the stool microbiota composition, gene expression, and microbiota

localization with respect to the epithelium. In addition, we will assess the impact of CMC exposure in the diet on markers of metabolic syndrome including response to oral glucose tolerance testing and other plasma metabolite measurements.

Healthy volunteers will be recruited for a 11-day in-patient study. All participants will receive 3 full days of freshly prepared emulsifier-free food to begin the study. This will be called the “washout period”. Participants will then be randomized into an “emulsifier-free” arm and a “CMC” arm.

Both arms will continue the same diet except that the “CMC” arm’s brownie and sorbet will have CMC added to achieve a level of 15 gm per person per day consumption, which are the levels of emulsifier consumption that can readily be achieved by humans who eat a large amount of processed foods. If the average American eats 2kg of processed food per day containing 2% emulsifier (the limit of individual emulsifiers), this would amount to 40g of emulsifiers per day. Serial collection of fecal, blood, urine and mucosal biopsy samples will define our ability to reliably quantitate CMC consumption by assay of biological fluids and preliminarily investigate the extent to which CMC consumption by humans impacts the gut microbiota and its interaction with the host parameters related to inflammation and metabolism.

3.2 Primary Study Endpoints

This is not an efficacy study. There are no pre-specified efficacy or safety endpoints for this study. Rather, we will use an unbiased approach to determine the composition of the microbiota and metabolome.

4 Participant Selection and Withdrawal

[figure not shown]
4.1 Inclusion Criteria

1. Participant is capable of giving informed consent
2. Participant is age 18 to 60 years

4.2 Exclusion Criteria

1. Diagnosis with IBD, celiac disease, or other chronic intestinal disorders. Since we are interested in assessing the impact of diet on the microbiome in the absence of pathologic inflammation, we will exclude participants with chronic intestinal abnormalities.

Figure 1. Schematic Study Outline

2. Baseline bowel frequency less than every 2 days or greater than 3 times daily. Normal bowel frequency is every 3rd day to 3 times per day.²⁰⁻²³ Although unknown, stool frequency could be related to the microbiome composition.²⁴⁻²⁶ Furthermore, change in diet could alter baseline stool frequency, potentially causing diarrhea, particularly in those with high baseline stool frequency, or severe constipation in those with low stool frequency. To avoid the need for use of antidiarrheal medications or laxatives, which themselves could alter the microbiome composition, these patients will be excluded.
3. Current smoker. What effect smoking has on the microbiome of the gut is unknown. Furthermore, because our hospital is a smoke-free environment, volunteers will not be able to smoke. Thus, inclusion of smokers would increase the risk of early withdrawal from the study.
4. Body Mass Index (BMI) <18.5 or >40 at screening. Volunteers with BMI below normal²⁷ will be excluded to prevent inclusion of participants with a subclinical systemic disease that may influence the gut microbiome. Volunteers with severe obesity will be excluded as obesity may be associated with altered gut microbiome composition.
5. More than two of the criteria for metabolic syndrome:
 - A waist circumference greater than 35 inches (89 centimeters) for women and 40 inches (102 centimeters) for men at screening.
 - A diagnosis of diabetes mellitus or baseline HbA1c > 6.4% or a fasting glucose level of greater than 100mg/dL
 - Systolic blood pressure >130 mmHg or diastolic blood pressure >85 mmHg or treated with medications for hypertension at screening.
 - Fasting triglycerides >149 mg/dl or treated with medications for hypertriglyceridemia
 - Fasting HDL cholesterol <40 mg/dl in men or <50 mg/dl in women or treated with medications for hypercholesterolemia
6. Known substance abuse disorder or consumption of illicit drugs or alcohol in the 24 hours prior to admission to the Center for Human Phenomic Science (CHPS).
7. Prior bowel resection surgery other than appendectomy. It is unknown how prior bowel resection surgery may influence the microbiome composition, hence we will exclude these participants.
8. Contraindication to flexible sigmoidoscopy and biopsies. Patients with suppressed white blood count may be at increased risk of systemic infection following sigmoidoscopy with biopsies. As such, participants with a WBC less than 3,500 or an absolute neutrophil count of less than 1,000 will be excluded. Patients with thrombocytopenia or with a coagulopathy may be at increased risk of bleeding complications after colonoscopic biopsies. As such, patients with a platelet count of less than 100,000 or an INR greater than 1.2 will be excluded from the study.
9. Estimated GFR<60ml/min/1.73m² based on measured serum creatinine concentration
10. Pregnant and lactating women. To avoid any risk to an unborn fetus or new born baby from changing the mother's diet, pregnant and lactating women will be excluded.

11. Use of antibiotics in the 6 months prior to Visit 2. A small proportion of bacteria may require 6 months to recover after treatment with antibiotics.²⁸
12. Use of antacids, NSAIDs, or dietary supplements in the week prior to Visit 2. NSAIDs have been associated with *C. difficile* colitis, although whether this is causative and whether this is mediated through changing the fecal microbiota composition is unknown.²⁹ Antacids could potentially alter the gut microbiota by changing the acid milieu or by altering fecal transit time. For our study purposes, multivitamins will not be considered dietary supplements.
13. Use of laxatives or anti-diarrhea medications in the two weeks prior to Visit 2.
14. Use of anticholinergics in the week prior Visit 2.
15. Use of narcotics in the week prior to Visit 2.
16. HIV infection, AIDS, or other known conditions resulting in immunosuppression - we will determine this by direct participant query; no formal testing will be done.
17. Allergies or intolerance to the components of the study diets.
18. Participant has experienced diarrhea within the two weeks prior to Visit 2. Diarrhea is defined as a change in bowel habits with an increased frequency or loose stools such that the stool could not be lifted with a fork.
19. Refusal to use a medically accepted method of birth control while participating in this study, such as a barrier method, hormonal contraceptives, implanted birth control devices, permanent methods (such as a vasectomy), and/or abstinence.
20. Vegans and Vegetarians.
21. Student or employee of any one of the investigators.
22. Anyone who cannot receive study payment (ie: visa)
23. Any condition that the investigator feels may limit the volunteer's ability to complete the study protocol.

4.3 Participant Recruitment and Screening

Our goal is to have 16 participants complete this study; however, it is anticipated we may need to screen up to 50 participants to meet our target enrollment.

Participants will be recruited through local and web-based advertising. We may also contact participants who have been enrolled in other studies under the same PI in the past if they have consented to future contact. Other participants may contact the research coordinator by phone or email in response to local paper flyers or web based advertisements (i.e.: craigslist). All advertisements will be approved by the local IRB before being used.

Potential participants will be pre-screened via telephone for eligibility prior to the screening visit. At the screening visit, potential participants will be screened for eligibility before being enrolled in the study. Potential participants will be directly queried regarding exclusion criteria. If there are questions regarding eligibility, relevant information from the participant's medical record will be obtained, with appropriate permission for release of records as necessary to comply with HIPAA. In the absence of any concerns, the participant's medical records will not be requested or reviewed as part of this study.

4.4 Early Withdrawal of Participants

4.4.1 When and How to Withdraw Participants

Participants may be withdrawn from the study at any time if the investigator or the participant believes that the participant's safety will be jeopardized by continued participation, or if the participant does not follow study procedures. Likewise, participants will be withdrawn from the study if they withdraw consent.

5 Study Intervention

All foods will be prepared within the CHPS's metabolic kitchen without emulsifiers (unless specifically added). All participants will follow the same Western style diet (i.e. the only difference being portion size). The macronutrient percentages of calories for the study diet will be 55% carbohydrate, 30% fat, and 15% protein. The diet will be composed of two menus that will be consumed on alternating days. Water, coffee and tea will be provided as desired. Participants will have access to additional food outside of the meals provided, however, the entire serving of the previous meal must have been consumed. The additional food provided outside of the scheduled meals will consist of the food from the same Western style diet provided for each meal.

For the three days prior to admission, participants will be eating an emulsifier free diet at home. Food will be provided by the CHPS metabolic kitchen. After admission to CHPS, no emulsifiers will be consumed prior to dinner on Day 1. Thus, accounting for the 8 hours of nil per os status prior to admission, all participants will have approximately 80 hours of emulsifier free washout time prior to administration of the food containing CMC.

Participants will be randomly assigned to receive 0 or 15 gm per day of CMC (8 participants in each arm of the study). Beginning with the dinner meal on Day 1, all participants will consume one serving of brownie or sorbet (15 gm) per day that contain 0 or 2.5 gm CMC per serving. The brownie and sorbet servings will be provided at all three scheduled meals and scheduled snacks. Prior to eating any other food on the study menu, participants must consume the brownie and sorbet servings.

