6.2.4.10 Recording of diet

Participants will begin their randomized diets following the oral glucose tolerance test and flexible sigmoidoscopy at dinner. Participants will be instructed to consume only the food provided and no other food. Participants must eat all of the brownie and servings of sorbet provided. Participants will have access to additional food outside of the meals provided, however, the entire serving of the previous meal must have been consumed. The amount of food consumed will be recorded on the case report forms.

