6.2.4.11 Timing of meals

The first meal will be served following the oral glucose tolerance test or after the flexible sigmoidoscopy. All scheduled snacks and meals will be provided following the oral glucose tolerance test except during the flexible sigmoidoscopy. Lunch will be served at approximately 12:30h and dinner at approximately 18:00h. A snack will be provided at 15:00h and 21:00h. Beginning at the dinner meal, all participants will consume one serving of brownie or sorbet (15 gm) per day that contain 0 or 2.5 gm CMC per serving. Participants will be expected to finish each meal by the time of their next meal. There will be no limitation on the time to consume snacks. All food must be consumed by midnight.

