6.2.5.6 Timing of meals

Breakfast will be served at 09:00h. Lunch will be served at approximately 12:30h and dinner at approximately 18:00h. A snack will be provided at 10:30h, 15:00h and 21:00h on Days 2-9. Participants will be expected to consume snacks by the next meal with the last snack consumed by midnight on Days 2-9. On Day 10, the 21:00h intervention snack will be provided in addition to the intervention and meal at 18:00h. Participants will be expected to finish each meal by the time of their next meal or snack. Lunch should be finished within 30 minutes. On Day 10, all food must be consumed by 19:30h. No food or beverage other than water is to be consumed between midnight and breakfast on Days 2-9 and between 19:30h and breakfast on Day 10.

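### The serving rule in Sections 5 and 6.2.4.11 gives 2.5 g of CMC per day as written, which contradicts the 15 g/day in six doses stated elsewhere

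*Combined protocol and SAP*

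**What the plan says.** The daily amount of CMC appears in three places:

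- Study Summary: participants receive "0 or 15 gm per day of carboxymethylcellulose in 6 divided doses baked in chocolate brownies and served in sorbet".
- Section 3.1: in the active arm the "brownie and sorbet will have CMC added to achieve a level of 15 gm per person per day consumption".
- Section 5: "Participants will be randomly assigned to receive 0 or 15 gm per day of CMC".

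The serving rule appears in two operative places. Section 5 says "all participants will consume one serving of brownie or sorbet (15 gm) per day that contain 0 or 2.5 gm CMC per serving". Section 6.2.4.11, the Day 1 meal instruction, repeats it: "Beginning at the dinner meal, all participants will consume one serving of brownie or sorbet (15 gm) per day", again with 0 or 2.5 g of CMC per serving.

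The sentence in Section 5 directly after the rule says "The brownie and sorbet servings will be provided at all three scheduled meals and scheduled snacks". For the main inpatient days, Section 6.2.5.6 sets breakfast, lunch and dinner and adds: "A snack will be provided at 10:30h, 15:00h and 21:00h on Days 2-9". Sections 6.2.4.10, 6.2.5.5 and 6.2.6.7 each instruct: "Participants must eat all of the brownie and servings of sorbet provided".

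On duration, Section 5 starts CMC at dinner on Day 1, and the inpatient stay ends on Day 11. Section 7.1 gives the Aim 1 detection rates (90% and 10%) as those seen after two weeks on the CMC and CMC-free diets.

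**The concern.** Three consecutive sentences in Section 5 cannot all be true. The first assigns 15 g/day, the second allows one 2.5 g serving per day, and the third provides servings at every meal and scheduled snack. The second is repeated in the section that staff would follow on Day 1.

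This is the rule for the only thing that is randomised. The first aim is to establish a way of administering and measuring CMC consumption, so the planned intake is the reference against which fecal and urinary CMC will be read. Adherence is defined as eating everything provided, so the number of servings is also needed to judge adherence.

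Two further ambiguities lie inside the same sentences:

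- The bracketed 15 gm could be the weight of a serving or the daily amount of CMC.
- The rule joins brownie and sorbet with *or*, while the next sentence joins them with *and*. The number of items eaten per occasion is therefore not fixed.

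The duration in Section 7.1 is a separate, smaller mismatch with the schedule.

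**Working it through.** **Daily CMC.** Formula: servings per day x CMC per serving.

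- The plan's own total: 15 g/day in 6 doses (Study Summary) gives 15 / 6 = 2.5 g per dose, which equals the stated CMC per serving.
- Six occasions: 3 meals + 3 snacks on Days 2-9 (Sections 5 and 6.2.5.6). One item each gives 6 x 2.5 = 15 g/day, which reproduces the stated total.
- The serving rule as written: 1 x 2.5 = 2.5 g/day. Against 15 g/day the ratio is 15 / 2.5 = 6.
- If a brownie and a sorbet were both eaten at each occasion, each with 2.5 g: 6 x 2 x 2.5 = 30 g/day. This only illustrates why the *or*/*and* difference matters; no section states 30 g.

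**The bracketed 15 gm.** As serving weight, CMC would be 2.5 / 15 = 16.7% of the serving. As daily CMC, the sentence would carry both 15 g per day and 2.5 g per serving, and only the single serving would not fit. The documents do not settle which is meant.

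**Duration of CMC exposure.** Start: Day 1 dinner, about 18:00 (Section 6.2.4.11).

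- To the last permitted food on Day 10, 19:30 (Section 6.2.5.6): 9 x 24 + 1.5 = 217.5 h; 217.5 / 24 = 9.06 days.
- To the latest discharge on Day 11, 17:00 (Section 6.2.6.11): 10 x 24 - 1 = 239 h; 239 / 24 = 9.96 days.
- The only 14-day period is the total time on study food: 3 emulsifier-free days + 11 inpatient days = 14 (Sections 1.3.1, 6.2.2 and 6.2.3.3).

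**Does the duration affect the 89% power?** Inputs from Section 7.1: n = 8 per group, 90% versus 10%. Section 7.1 does not state the test or alpha for this calculation, so two-sided 5% is assumed. Pooled z test with continuity correction:

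- Corrected difference: 0.80 - 1/8 = 0.675.
- Null standard error: sqrt(0.5 x 0.5 x 2/8) = 0.25.
- Alternative standard error: sqrt((0.9 x 0.1 + 0.1 x 0.9)/8) = 0.15.
- Power: Phi((0.675 - 1.96 x 0.25)/0.15) = Phi(1.23) = 0.891.

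This reproduces the stated 89%. Other common methods give more (Fisher exact 93.2%, arcsine 96.0%, uncorrected z 98.1%). Duration is not an input to any of them.

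**The case against.** The strongest reply is that the documents largely resolve the matter themselves. The sentences on either side of the rule give 15 g/day and servings at all meals and snacks. The Study Summary gives six doses, and Section 6.2.5.6 gives six occasions on Days 2-9. The recording-of-diet sections speak of servings in the plural. A metabolic kitchen prepares the food, and the amount eaten is recorded on the case report form.

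Most of that stands. A reader might infer that participants would in practice receive only 2.5 g/day. The documents do not support that inference, because the surrounding text points to several servings a day. The reply does not remove the contradiction, however. The sentence is in current operative text, it appears twice, and the agreement at 15 g rests on one item per occasion, which the text does not say.

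A reader might also infer that serving counts on Days 1, 10 and 11 are contradictory. They are not. A dinner start makes Day 1 a partial day. On Day 10 the 21:00 intervention snack is moved to 18:00, which suggests that the daily count is kept, although the three-snack list names only Days 2-9. On Day 11 the occasions are simply not listed, and the glucose tolerance test and fasting samples come before any food that day. These are requests for completeness.

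On duration, it is fair to say that Section 7.1 describes both arms, and that 14 days does fit time on emulsifier-free food in the control arm. The mismatch concerns the CMC arm only.

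**Conclusion.** The serving rule in Sections 5 and 6.2.4.11 contradicts the daily CMC amount in the Study Summary, Section 3.1 and Section 5. It also contradicts the six divided doses and the provision at every meal and snack. As written the difference is 2.5 against 15 g/day, six-fold. The figures agree at 15 g on Days 2-9 if there are six occasions with one item at each; that assumption is not stated. The sentence defines the randomised exposure and should be fixed. The review takes no position on which figure is right.

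The two weeks in Section 7.1 is a minor wording point: scheduled CMC exposure is about 9.1 to 10.0 days. A reader might infer that the Aim 1 power is therefore wrong or that the detection rates are undermined. The documents do not support either reading. The 89% reproduces under an assumed two-sided 5% test and does not use duration, and Section 7.1 does not derive the 90% and 10% from duration-specific data. The 11 days of administration in the Study Summary is a calendar count and is not in question.

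**What to change.** Reconcile the Study Summary and Sections 3.1, 5, 6.2.4.11 and 6.2.5.6 to one statement of:

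- servings per day;
- items per occasion (brownie, sorbet or both);
- CMC per serving;
- CMC per day.

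Say what the bracketed 15 gm refers to. It would help, though it is not essential, to list the intended serving occasions on Days 1, 10 and 11 in the same place. In Section 7.1, bring the duration into line with the scheduled CMC exposure; the power figure needs no change.

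The cost is protocol wording only, with no new procedures, data or analyses. The choice of figures belongs to the investigators.
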